Properties of myocardial microcirculation in patients with different pathomorphological substrates, before and after recanalization of coronary artery chronic total occlusion

March 28 th, 2017.

BACKGROUND

Chronic total occlusion (CTO) is defined as a complete occlusion of the coronary artery without blood flow (TIMI 0) in the occluded segment, which lasts longer than 3 months (1). In various published series, the prevalence of CTO lesions in patients with coronary artery disease is between 20-30% (2-4). In a large Canadian registry with over 16,000 subjects, the prevalence of CTO lesions on diagnostic coronary angiography was 18.4% of all angiographically significant coronary stenoses (5).

This coronary lesion group is especially recognized as technically most complex coronary lesion subset for percutaneous revascularization. The success of percutaneous revascularization of these lesions has been only 60-70% until recently, which is significantly lower than the revascularization of non-occlusive lesions, which is successful in as many as 98% of cases (5,6). Over the past decade, significant advances have been made in the technology, equipment, and techniques of percutaneous revascularization procedures for the treatment of CTOs, which, with increasing operator experience, have resulted in procedural success rates of about 90% (7-9).

The particular functional characteristics of CTO lesions are the existence of collateral blood vessels, and smaller or larger amount of viable myocardium in the area of its vascularization. The complex interplay of these two factors depends on the overall coronary physiology and influence the clinical manifestations in the patient.

Collaterals are interarterial connections that allow blood flow from the donor artery to the vascular territory that belongs to the occluded epicardial artery. In this manner, the integrity of the myocardium supplied by the occluded coronary artery can be preserved partially or even completely (10). However, although at rest collateral blood flow can provide preservation of the viability and even contractile capacity of the myocardium, it is considered that collateral flow during exertion is not sufficient in up to 90% of cases (11).

Collaterals develop in the process of arteriogenesis through the "recruitment" of preformed and preexisting interarterial connections, in a process that depends largely on the hemodynamic shear stress along the pressure gradient (between the unoccluded and occluded artery) that occurs in the case of coronary artery occlusion, and the presence of a viable myocardium is not necessary for the development of collaterals (10,12).

Numerous studies have been published to date that examined the functional parameters of occluded (and recanalized) coronary artery microcirculation (10,11,13–18), while data on the potential effects of CTO recanalization on collateral flow and collateral donor physiology are scarce. In the presence of CTO, if the myocardium in the area of the occluded artery is perfused with significant blood flow through the collateral bloodstream, the CTO recanalization and the establishment of normal antegrade flow results in a rapid decrease or termination of the collateral flow, and decrease flow in the donor artery, which may alter circulatory parameters of donor artery itself (e.g. fractional coronary flow reserve - FFR, coronary flow reserve - CFR, etc.). *Werner* and co-workers have elegantly demonstrated that collateral flow provides about 50% of

the antegrade flow that is established after CTO recanalization (17). The collateral function decreases rapidly after opening the CTO, and practically after a little more than 30 minutes after the establishment of antegrade flow reaches the lowest level that is maintained even after 24 hours from the intervention (17,19). It is not yet clear enough and there is insufficient published data on the contribution of collateral flow to coronary artery donor physiology. Thus, Werner et al showed that the FFR in the artery donating collateral for CTO was 0.82 ± 0.11 in 18 patients who did not have angiographically significant stenosis on the donor artery (15). In this way, they showed that small angiographic irregularities or mild diffuse coronary disease in the case of large coronary flow (caused by developed collateral blood flow) can give a significant drop in pressure in the arterial tree near the border defined for the existence of ischemic lesions. Furthermore, several cases have been reported in the literature in which there were significant changes in the FFR value in the donor artery after successful CTO recanalization, which in some cases led to a change in the indication for revascularization by moving from a FFR value <0.80 to values ≥0.80 (20-24). It is unclear to what extent these cases represent the broader population of CTO patients and whether they can be generalized. "Publication bias" where relatively rare occurrences that show major changes in the expected direction are more likely to be published than smaller ones or changes in the unexpected direction (25, 26). To our knowledge, only two studies to date have been published on a large number of patients examining the impact of CTO reanalysis on FFR in the non-occluded arteries. In a study of 14 subjects who had a CTO recanalized, 6 of 9 patients with initial ischemic FFR in the donor artery experienced a change in FFR to the non-ischemic range (FFR before PCI 0.76 ± 0.04 and after PCI 0.86 ± 0.03) (27). Recently, the largest and most important study was published with 34 patients examining the impact of CTO recanalization on the functional parameters of non-occluded vessels (28). This study confirmed that after successful CTO recanalization, there is a modest increase in FFR (0.810 versus 0.782) in the collateral donor artery, as well as a reduction in coronary flow therein (28). Recently, a group of Japanese authors also proposed an in vitro model to test the effect of collateral flow on the circulation of the donor artery and the recipient of the collateral flow, with a complex mathematical model and formulas describing the effect of the collateral recipient's blood vessel revascularization on the function of the collateral donor blood vessel (29). Non-invasive measurement of coronary flow reserve before and after CTO reanalysis has been reported in only one study so far, which in a series of 24 patients showed that after successful recanalization of the CTO of the right coronary artery, there was an increase in coronary flow reserve (CFR) after 3 months of intervention (2.3 ± 0.3 vs 1.8 ± 0.3 ; p < 0.001), whereas in the immediate postprocedural period (within 24h of PCI), the CFR value through the LAD artery did not increase $(1.8 \pm 0.3 \text{ vs } 1.8 \pm 0.2, \text{ p} = 0.89).$

Previous studies have not sufficiently examined the relationship between collateral flow changes after PCI for CTO and changes in functional parameters of the donor artery with the amount of viable myocardium and segmental function of the left ventricle after revascularization. Also, the association of the phenomenon of coronary theft with the viability and occurrence of inducible myocardial ischemia has not been sufficiently investigated.

WORKING HYPOTHESIS

- 1. Following successful recanalization of chronic total coronary artery occlusion, the hemodynamic microcirculatory parameters (CFR, FFR, HMR) in the non-occluded (collateral donor) coronary artery will change as compared to the values before the procedure.
- 2. The magnitude of change in these parameters depends on the size of the collateral blood flow to the territory of the occluded coronary artery and the amount of viable myocardium in the vascularization zone of the occluded artery.

OBJECTIVES OF THE RESEARCH

- 1. The primary goal of the study is to determine the magnitude and direction of change in the functional parameters of microcirculation in collateral donor coronary artery after the successful opening of the chronic total occlusion.
- 2. The secondary goals of the study are:
- a) determination of the factors on which the change in hemodynamic parameters of the nonoccluded arteries depend,
- b) determining the factors that influence the improvement of segmental kinetics of the left ventricle after six months from the recanalization of the occluded artery,
- c) determination of correlation of functional parameters of microcirculation with ischemia, viability and segmental kinetics of the left ventricle,
- d) determining the correlation (change) of microcirculatory functional parameters with the quality of life determined by the Seattle Angina Questionnaire.

STUDY PROTOCOL

A. Data collection before intervention

In all patients, the following tests will be performed in the period before the intervention:

- Electrocardiogram,
- Echocardiographic examination,
- Stressechocardiographic test,
- Measurement of coronary flow reserve for collateral donor artery (RCA or LAD) by non-invasive transthoracic Doppler echocardiography,
- Scintigraphy (SPECT) for detection of viable myocardium in the CTO area,
- Seattle Angina Questionnaire

B. Data collection during PCI for CTO

At the beginning of the procedure, after administration of nitroglycerin intracoronary (200 μ g), angiography will be performed with optimal visualization of epicardial coronary circulation and collateral blood flow to the area vascularized by the occluded artery. Angiographic quantification of collateral and collateral flow will be performed according to Rentrop and CC classifications

(16,30). Quantitative coronary angiography (QCA) will be used to quantify all coronary stenoses except CTO, which by definition is 100% stenosis.

Before the CTO recanalization, after adequate heparinization of the patient (by administration of 100 IU / kg heparin intravenously), the following functional parameters will be measured in each of the two non-occluded coronary arteries using a coronary wire with pressure and flow sensor (Combowire; Volcano Corp, San Diego, CA):

- Basal blood flow velocity

- Hyperemic blood flow velocity

- Coronary flow reserve (CFR)

- Mean blood pressure in the aorta (Pa) and at the sensor position (Pd)

- Fractional flow reserve (FFR)

- Hyperemic microvascular resistance (HMR)

Hyperemia will be caused by the administration of an intravenous infusion of adenosine ($140\mu g / kg / min$).

Following this, the CTO will be opened, using standard contemporary strategies and materials. After passage of the occlusion with the antegrade wire, a coronary wire with pressure and flow sensor will be introduced distally to the occlusion, and hyperemia will be induced by administering adenosine intravenously. After measuring the above functional parameters at this location, CTO dilatation and stent implantation will be initiated. Successful percutaneous coronary intervention (procedural success) is defined as the establishment of TIMI 3 flow with a residual stenosis of less than 30% after stent implantation or balloon dilatation. In the case of procedural success, the previously described functional parameters will be measured in the recovered coronary artery using the coronary wire with pressure and flow sensors when administered adenosine intravenously.

Finally, to evaluate the effect of CTO opening on the physiological parameters of the nonoccluded arteries, all the functional measurements mentioned above will be repeated with the same (or closest possible) sensor positions in both non-occluded arteries, as described in detail above.

C. Data collection in the procedure

The following examinations will be performed in all patients who have achieved procedural success:

- *Within the first 24 hours of intervention*: measurement of coronary flow reserve for LAD and RCA artery by non-invasive Doppler echocardiography,

- 6 months after the intervention:

- Electrocardiogram
- Echocardiographic examination

- Measurement of coronary flow reserve for LAD and RCA artery by non-invasive Doppler echocardiography

- Seattle Angina Questionnaire
- Information on possible adverse cardiovascular events from intervention to follow-up (MACE)

- Catheterization of the heart if clinically indicated

MEASUREMENT AND DEFINITION

- The procedural success of recanalizing chronic total occlusion.

Successful percutaneous coronary intervention (procedural success) is defined as the establishment of TIMI 3 flow with residual stenosis of less than 30% after stent implantation or balloon dilatation.

- TIMI flow is a scale that semi-quantifies antegrade flow through the coronary artery as follows: TIMI 0 - no antegrade flow behind occlusion; TIMI 1 - there is a flow behind the occlusion site with incomplete filling of the distal coronary artery; TIMI 2 - slow antegrade flow that completely fills the distal artery; TIMI 3 - Normal coronary flow with complete filling of distal artery (31).

- Rentrop classification of collateral flow (30) is a widely used angiographic system that does not describe the characteristics of collateral blood vessels themselves, but their effect on filling the occluded artery distal to the site of occlusion. There are 4 grades of collateral flow according to this classification: Rentrop 0 - no filling of the occluded vessel via collateral blood flow, Rentrop 1 - filling only the lateral branches of the occluded vessel without filling the main epicardial blood vessel, Rentrop 2 - partial filling of the main epicardial blood vessel, and Rentrop 3 - completely filling the major epicardial blood vessel.

- Semi-quantitative classification of collateral vessels (collateral connections) (16): CC0 - no continuous connections, CC1 - continuous collateral threadlike connections, CC2 - lateral branches (diameter \geq 0.4mm). CC3 - Direct connections \geq 1mm in diameter.

- The Seattle Angina Questionnaire is a modern and validated instrument for assessing the quality of life in patients with coronary disease (32). This questionnaire is based on five different domains that are assessed in patients: physical limitation, anginal stability, anginal frequency, treatment satisfaction and disease perception.

- Myocardial scintigraphy - All patients will have a 740 MBg 99mTc-MIBI myocardial scintigraphy given intravenously 10-15 minutes after sublingual administration of 0.5mg nitroglycerin (33) before attempting to recanalize the occlusion. The recording will take place 45-60 minutes after the administration of the radiopharmaceuticals, in a supine position, with a single gamma camera equipped with a high-resolution low energy collimator. 64 projections will be taken in the 180-degree range (starting from 45 degrees from the right front oblique to 45 degrees from the left rear position). After the reconstruction of the image, semi-quantification of myocardial perfusion and function will be done software. The size and severity of the perfusion defect will be calculated based on a 17-segment radiopharmaceutical uptake model and based on a guide from the European Nuclear Medicine Association and the European Association of Cardiologists for radionuclide imaging of cardiac function (34). The total download score of MIBI radiopharmaceuticals (SRS) will be calculated. The size and severity of the perfusion defect will also be indicated according to each of the three major vascular territories: anterior descendant, circumflex, and right coronary artery. Assessment of regional left ventricular wall thickness will be assessed by visual inspection in the Chinese mode of SPECT perfusion images (34). The presence of viable myocardium in the infarct zone will be considered as the absorption of radiopharmaceuticals \geq 55% of normal perfusion, with left-wall wall thickness gain (35–37). Also, the left ventricular ejection fraction, end-diastolic volume, and end-systolic volume will be evaluated using an automated algorithm (38).

- Echocardiography - Transthoracic echocardiographic examination will be performed in all subjects. All standard echocardiographic sections will be made. Measurements from orthogonal apical sections ("two and four cavities") will be used to estimate the global function of the left ventricle, with the simulation fraction calculated using the Simpson method. A 17-segment

model will be used to calculate the wall motion score index of the left ventricular segment, while segmental kinetics will be constructed as follows: 1-normal segment kinetics, 2-hypokinesia, 3-akinesia, and 4- dyskinesia. This score will be calculated by dividing the sum of the mobility levels of the individual segments by the total number of visualized segments (39).

Stressechocardiographic test - a submaximal, symptom-limited stress-echocardiographic test on a Bruce protocol will be performed in all subjects. Before the test, at the end of each load step, and after the test is completed, arterial blood pressure and SF will be measured. The criteria for discontinuation of the test are: onset of anginal problems, fatigue, reaching submaximal frequency, the onset of ST depression greater than 1 mm, and the onset of hypertensive reaction (blood pressure greater than 240/130 mmHg). According to the protocol of the stressechocardiographic test, an echocardiographic examination in the left decubital position will be done to everyone before and immediately after the test. The test was defined as positive for the presence of inducible myocardial ischemia if there was a deterioration of left ventricular segmental kinetics at the EHO after the test.

- Measurement of coronary flow reserve for LAD artery - Transthoracic Doppler echocardiographic examination will record blood flow velocities in the LAD artery, at rest and after induction of hyperemia by administering adenosine intravenously (0.14 mg/kg/ min). Coronary flow reserve will be calculated as the ratio of maximum hyperemic and maximum basal flow rate (40).

- The following invasive functional parameters will be determined for all subjects where technically feasible:

- Basal blood flow velocity

- Hyperemic blood flow velocity
- Mean blood pressure in the aorta (Pa) and at the sensor position (Pd)
- Coronary flow reserve (CFR)
- Fractional flow reserve (FFR)
- Hyperemic microvascular resistance (HMR)

- Procedural complications - All patients will be monitored for the occurrence of periprocedural complications, including myocardial infarction, coronary perforation, cardiac tamponade, emergency cardiac surgery, complications at the site of vascular access.

- Adverse cardiovascular events during the follow-up period - All patients will be monitored for adverse cardiovascular events during the follow-up period: cardiovascular death, non-fatal myocardial infarction, and any recurrent myocardial revascularisation.

SAMPLE SIZE

Based on the primary goal of the study, the required number of subjects was calculated according to the appropriate formula for Student's t-test for related samples using the following assumptions and data from previous published research: statistical power $(1-\beta) = 0.80$; statistical significance (α) = 0.05; expected change (increase) of coronary flow reserve (CFR) in the donor artery after opening of chronic total occlusion of 0.5 (41-43), expected standard deviation for invasive Doppler CFR in the reference artery of 0.85 (44).

$$n = \frac{(Z_{1-\frac{\alpha}{2}} + Z_{1-\beta})^2 \cdot \sigma^2}{\delta^2} = \frac{(1,960 + 0,842)^2 \cdot 0.85^2}{0,5^2} = 22,7 \approx 23$$

The sample size we calculated to be 23 patients, based on the above assumptions. Taking into account that the success of the procedure of opening a chronic total occlusion at the Cardiology Clinic of the Clinical Center of Serbia is 90% and that 15% of the respondents will be unavailable for a six-month follow-up, a total of 30 patients should be included.

STATYSTICAL ANALYSIS

- The following statistical methods will be used for data description:

Mean, median, standard deviation, interquartile range

- The following methods of analytical statistics will be used:

chi-square test, Student's t-test for independent and related samples, correlation, linear regression, logistic regression, The ROC curve and C-statistics will be used to determine the cut-off values. All tests will be realized as two-way. A p-value of <0.05 will be considered statistically significant. Data analysis will be done in the SPSS statistical software package (version 19 or above).

References:

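### Inducible ischaemia is recorded as one whole-ventricle yes/no, so the ischaemia part of objective 2c cannot separate donor-territory from CTO-territory ischaemia

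*Combined protocol and SAP*

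**What the plan says.** - **Objective.** Secondary objective 2c in OBJECTIVES OF THE RESEARCH is "determination of correlation of functional parameters of microcirculation with ischemia, viability and segmental kinetics of the left ventricle". It names no artery.
- **Ischaemia measure.** In MEASUREMENT AND DEFINITION, the "stress-echocardiographic test on a Bruce protocol will be performed in all subjects", and "an echocardiographic examination in the left decubital position will be done to everyone before and immediately after the test". The result is then made binary: "The test was defined as positive for the presence of inducible myocardial ischemia if there was a deterioration of left ventricular segmental kinetics".
- **Physiological measures.** Section B of STUDY PROTOCOL measures flow velocities, CFR, FFR and HMR separately in each of the two non-occluded arteries before recanalization, and distal to the occlusion once the wire has crossed and before dilatation. All are repeated after success.
- **Segment grading.** The echocardiography paragraph sets a 17-segment model in which "segmental kinetics will be constructed as follows: 1-normal segment kinetics, 2-hypokinesia, 3-akinesia, and 4- dyskinesia", with the index averaged over visualized segments. It does not say that this grading is applied to the post-exercise images.
- **Territories.** Only the SPECT paragraph reports by territory: "The size and severity of the perfusion defect will also be indicated according to each of the three major vascular territories". SPECT is listed before the intervention as "Scintigraphy (SPECT) for detection of viable myocardium in the CTO area", and no stress acquisition is described for it.
- **Background.** BACKGROUND remarks that "it is considered that collateral flow during exertion is not sufficient in up to 90% of cases". It closes by naming the link between coronary steal and inducible ischaemia as insufficiently studied.

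**The concern.** Each patient has up to three arteries with their own pre-opening values and one ischaemia label shared by all of them. A positive test may come from the bed of the occluded artery, the bed of the donor artery, or both, and the recorded result does not say which. If donor-artery CFR, FFR or HMR is compared between test-positive and test-negative patients, any relation found cannot be attributed to donor-territory ischaemia. A null result may only mean that the label was driven by the other bed. The label also discards extent: one worsening segment counts the same as many.

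A second, conditional problem is balance. A two-group comparison in about 30 patients weakens quickly if nearly all of them fall in one group. If segment grades after exercise are never recorded, the information needed to repair either problem may be missing from the dataset.

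**Working it through.** **1. The plan's own sample size (SAMPLE SIZE).** Inputs: change in CFR 0.5, SD 0.85, two-sided alpha 0.05, power 0.80.

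n = (1.960 + 0.842)² × 0.85² / 0.5² = 22.7, so 23, as stated. Inclusion: 23 / (0.90 × 0.85) = 30.07, against 30 stated. This calculation covers the primary paired comparison only; nothing is sized for 2c. I use N = 30 because the stress test is planned in all subjects before the procedure.

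**2. Attribution.** No arithmetic is needed. The exposure side of 2c is per artery, and the ischaemia side is per patient with no territory rule. SPECT does not fill the gap, because it reports by territory but is planned for viability. This defect does not depend on any positivity rate.

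**3. Contrast, over an assumed range.** The documents state no expected stress-echo positivity, so the share positive is an assumption. With n₁ positive and n₀ negative:

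- standard error of a difference in means, in SD units: √(1/n₁ + 1/n₀)
- equivalent number of evenly split patients: 4 / (1/n₁ + 1/n₀)

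For example, at 27 vs 3: 1/27 + 1/3 = 0.370, so SE = 0.61 and the equivalent number is 4 / 0.370 = 10.8.

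The last two columns use a two-sided two-sample t-test with SD 0.85. Borrowing 0.5 as a between-group CFR difference is also an assumption.

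| Assumed positive | Split | SE (SD units) | Equivalent even-split N | Power for CFR difference 0.5 | Difference detectable with 80% power |
|---|---|---|---|---|---|
| 50% | 15 / 15 | 0.37 | 30 | 34% | 0.90 |
| 60% | 18 / 12 | 0.37 | 28.8 | 33% | 0.92 |
| 70% | 21 / 9 | 0.40 | 25.2 | 30% | 0.98 |
| 80% | 24 / 6 | 0.46 | 19.2 | 24% | 1.13 |
| 90% | 27 / 3 | 0.61 | 10.8 | 15% | 1.50 |

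Imbalance costs little up to about 70% positive and a great deal at 90%. Even the perfect split has only 34% power, so the sample size is a limit in every row.

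**4. What a graded score could detect.** By Fisher's z, detectable |r| = tanh[(1.960 + 0.842) / √(N − 3)]:

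- N = 30: tanh(2.802 / 5.196) = 0.49
- N = 27 (0.90 × 30): 0.52
- N = 23: 0.56

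These figures are for an ordinary correlation and are a guide only for a rank correlation. They no longer depend on the number of test-negative patients, but they need real spread in the score.

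**The case against.** The strongest reply has four parts.

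- **The 90% figure is not a positivity rate.** A reader might infer that the protocol expects about 27 of 30 patients to test positive, leaving 2c with almost no contrast. The documents do not support this. The figure is an upper bound, it concerns collateral flow, and it stands in the background. The test is submaximal and may stop for fatigue, and BACKGROUND says that the amount of viable myocardium in the CTO territory varies, so positivity could be well below 90%. This stands.
- **2c is wider than ischaemia.** Its viability and segmental-kinetics parts rest on SPECT and wall-motion scores, not on this label. This stands.
- **2c is not confined to the donor artery and does not ask about change.** The CTO artery is measured too, and for it a label driven by the CTO bed is relevant. Objective 2d mentions change and 2c does not, so a baseline-only stress test is no fault under 2c. This stands. The steal sentence describes a gap in earlier work and is not itself an objective.
- **The territory gap is in the definition, not necessarily in the data.** Images are taken before and after exercise and a segment scale exists. This also stands, and it is why the repair is cheap.

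None of this removes the attribution problem: whichever artery is analysed, the label cannot say which bed was ischaemic.

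**Conclusion.** The concern holds in limited form. As defined, the ischaemia variable cannot separate donor-territory from CTO-territory ischaemia and discards extent. That follows from the text alone.

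The loss of contrast is conditional. Over an assumed 60% to 90% positive, 30 patients are worth about 29 down to 11 evenly split patients, and the documents do not say where in that range, or below it, the trial will fall. The claim that the ischaemia comparison must fail for lack of negatives is not established.

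The point touches one element of one secondary objective. The primary objective and its sample size are unaffected. It is a worthwhile, inexpensive improvement and not a flaw that threatens the trial.

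**What to change.** 1. Grade all 17 segments (1–4) on both the pre-exercise and the immediate post-exercise images.
2. Prespecify which segments belong to LAD, Cx and RCA, the three territories already used for SPECT. The echocardiography paragraph has no such assignment. State how the donor artery is identified if both non-occluded arteries supply collaterals.
3. For the ischaemia part of 2c, use the mean change in grade over segments visualized at both time points, separately for the CTO and donor territories. A mean is preferable to a raw sum, which depends on territory size and on how many segments can be read.
4. Correlate each territory score with the pre-opening CFR, FFR and HMR of the matching artery. Also correlate the donor-artery parameters with the CTO-territory score, which is the comparison closest to the steal question. Use rank correlation, since scores may cluster at zero.
5. Keep the positive/negative result as description, and label these correlations exploratory.

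**Cost.** Wording, some extra scoring work, and no new test, visit or patient. Some post-exercise segments will be unreadable. There are at least nine correlations (three parameters for each of two matching pairs, plus three cross-territory), hence the exploratory label. The power gain is only moderate; what is gained is chiefly the ability to say which territory was ischaemic.

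### The sample size combines a CFR gain, an SD and a loss allowance that do not belong to one measurement, so the stated 80% power is not supported for the in-procedure comparison

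*Combined protocol and SAP*

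**What the plan says.** - **Sizing (SAMPLE SIZE).** The section says that "the required number of subjects was calculated according to the appropriate formula for Student's t-test for related samples". Its inputs are 80% power, "statistical significance (α) = 0.05" and an "expected change (increase) of coronary flow reserve (CFR) in the donor artery after opening of chronic total occlusion of 0.5 (41-43"). The SD is 0.85, described as that of invasive Doppler CFR in the reference artery. The result is 23 patients, raised to 30 for 90% procedural success and 15% unavailable at six months. No time point is given for the change. STATISTICAL ANALYSIS adds "All tests will be realized as two-way".
- **Invasive CFR (STUDY PROTOCOL, part B).** It is measured in the non-occluded arteries before the occlusion is opened. At the end of the same procedure, "all the functional measurements mentioned above will be repeated with the same (or closest possible) sensor positions in both non-occluded arteries".
- **Later CFR (STUDY PROTOCOL, part C).** Within 24 hours the plan has "measurement of coronary flow reserve for LAD and RCA artery by non-invasive Doppler echocardiography", and the same measurement is listed again at six months. Catheterization at six months is done only on clinical indication.
- **Prior data (BACKGROUND).** One non-invasive study of 24 patients with recanalized right coronary occlusions reports CFR of 2.3 ± 0.3 vs 1.8 ± 0.3 at three months (p < 0.001). For the first day the protocol states: "whereas in the immediate postprocedural period (within 24h of PCI), the CFR value through the LAD artery did not increase". The figures behind that statement are 1.8 ± 0.3 and 1.8 ± 0.2, with p = 0.89.
- **Primary goal (OBJECTIVES OF THE RESEARCH).** It concerns the size and direction of change in donor-artery microcirculatory parameters. It fixes no single parameter, method or time point.

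**The concern.** A sample size calculation supports a power statement only if its effect, variability and attrition describe the same comparison. Here the SD points to the wire measurement, which exists only during the procedure. The loss allowance points to six months, where CFR is transthoracic. The 0.5 agrees numerically with a three-month transthoracic gain, and the same study found no gain in the first day.

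Two things are at stake. First, if the in-procedure invasive change is taken as primary, 80% power for 0.5 has no acute figure behind it in the documents, and power falls quickly for smaller gains. Second, with neither time point nor method fixed, the same trial could report an in-procedure or a six-month CFR change as its primary result, and the choice could be made after the data are seen.

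**Working it through.** **1. The plan's own figure.** Inputs from SAMPLE SIZE: z = 1.960 and 0.842, SD 0.85, change 0.5.

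n = (1.960 + 0.842)² × 0.85² / 0.5² = 22.69, rounded up to 23. This reproduces. The normal formula is slightly optimistic for a paired t-test: with the noncentral t distribution, 23 pairs give 76.9% power and 25 pairs are needed for 80%.

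Inflation: 23 / (0.90 × 0.85) = 30.07, stated as 30.

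**2. Which measurement does each input belong to?**

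| Input | Value | Setting it fits |
|---|---|---|
| SD | 0.85, invasive Doppler | In-procedure only |
| Effect | 0.5 | No time stated; equals the three-month transthoracic gain in BACKGROUND, 2.3 − 1.8 |
| Loss | 15% at six months | Late endpoint only |

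Under an in-procedure reading, the effect has no acute support in the documents and the six-month loss does not apply. Under a six-month reading, the SD comes from a different method. Neither reading makes all three inputs consistent.

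**3. What the 24-hour data allow.** The mean change is 1.8 − 1.8 = 0. The SD of the paired change is √(s₁² + s₂² − 2r·s₁·s₂) with s₁ = 0.3 and s₂ = 0.2. The within-patient correlation r is not given, so I assume 0 to 0.5. The SD of change is then 0.36 (r = 0) to 0.26 (r = 0.5). With n = 24 and t = 2.069, the 95% half-width is 0.15 to 0.11. These transthoracic data exclude a gain near 0.5 within 24 hours.

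**4. Power of the in-procedure comparison.** Paired t-test, two-sided 0.05, noncentrality = change / 0.85 × √n. Expected evaluable patients: 23 as planned, or 30 × 0.90 = 27 if six-month loss does not apply. Gains of 0.1 to 0.3 are assumed values; the documents give only about 0 (within 24 hours) and 0.5 (three months).

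| True gain | n = 23 | n = 27 |
|---|---|---|
| 0.5 | 77% | 84% |
| 0.3 | 37% | 42% |
| 0.2 | 19% | 22% |
| 0.1 | 8% | 9% |

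By the plan's own normal formula, the detectable change at 80% power is 2.802 × 0.85 / √n, which is 0.50 for 23 and 0.46 for 27.

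**5. The six-month reading.** Using the three-month SDs (0.3 and 0.3) as a stand-in, the SD of change is 0.42 (r = 0) to 0.30 (r = 0.5). Power for 0.5 with 23 pairs then exceeds 99%. This is not a like-for-like contrast with step 4, because the SD changes as well as the time point.

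**6. The SD itself.** The 0.85 is presented as the SD of CFR in an artery. The SD of a paired change is 0.85 × √(2(1 − r)) if both occasions have that SD, so it equals 0.85 only at r = 0.5. It is 1.20 at r = 0 and 0.54 at r = 0.8. Power for 0.5 with 23 pairs is then 48% and 99% respectively.

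**The case against.** A reader might infer that the trial is sized on a measurement taken minutes after opening, when no gain exists, and so is likely to miss its effect. The documents do not support that.

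- **The time point is open.** SAMPLE SIZE does not choose the in-procedure measurement, and its six-month allowance points the other way. Under a six-month reading, 0.5 is consistent with BACKGROUND. Part B states no interval in minutes.
- **The null result is borrowed.** It is transthoracic, within 24 hours, from 24 patients with right coronary occlusions. Applying it to wire CFR at the end of the procedure is an assumption. BACKGROUND also reports a rise in donor FFR (0.782 to 0.810) with reduced donor flow after recanalization, and a fall in collateral function to its lowest level in little more than 30 minutes. An acute comparison therefore has a rationale.
- **The source link is only numerical.** SAMPLE SIZE credits 0.5 to references 41-43, and the BACKGROUND study carries no reference number.
- **A true acute change of zero is not a missed effect.** The 5% rejection rate there is the type I error. The primary goal asks for magnitude and direction, which a null acute estimate would answer.
- **The SD drives much of the low power.** With the transthoracic 24-hour SDs in step 3, 23 pairs give about 72% to 93% power for a gain of 0.2, against 19% at SD 0.85.

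All of this stands and limits the point. None of it puts the effect, SD and attrition in one setting, or supplies an acute source for 0.5.

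**Conclusion.** The concern holds as an inconsistency in the sizing, not as a prediction that the trial will fail. No single time point and method fits all three of the 0.5 gain, the invasive SD of 0.85 and the 15% six-month loss. The arithmetic to 23 and 30 is otherwise reproducible.

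For the in-procedure comparison, the claimed 80% power depends on an acute gain of 0.5 that nothing in the documents supports. How far power falls depends on assumptions: the true acute invasive gain is unknown, 0.85 is treated as the SD of the paired change, and 23 or 27 patients are evaluable. For the six-month comparison, power may be ample, but that rests on a three-month study and an assumed correlation, and the plan's SD would still be the wrong one.

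**What to change.** Before analysis, state one time point and one method for the primary donor-artery CFR comparison. Take the expected effect, the SD of the paired change and the attrition from that setting. Either choice is defensible:

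- **In-procedure invasive CFR as primary.** Drop the 0.5 unless an acute source supports it. Remove the six-month loss from this calculation, and restate the detectable change and power for about 27 evaluable patients.
- **Six-month transthoracic CFR as primary.** Replace the invasive SD with a transthoracic SD of change, and justify the six-month effect, since the only late figure given is at three months. Report in-procedure CFR, FFR and HMR separately as acute results. MEASUREMENT AND DEFINITION describes the transthoracic method for the LAD only, so the RCA method should be added.

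In neither case should the plan declare in advance that a null acute result carries no weight: the first working hypothesis sets no late time point.

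The cost is wording. Both measurements are already scheduled. The small downside is that the stated power or detectable effect may look less favourable.
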